6.2 IMPORTANT PROTOCOL DEVIATIONS

No per protocol set analysis will be performed for this study; however, the following list in Table 6.2: 1 defines the different categories of potentially important protocol deviations (IPD), and it shows whether patients will potentially be excluded from evaluations performed in this trial. Potentially important protocol deviations will be handled according to BI standards (6), and the proportion of patients with IPDs will be presented for completeness purposes and to demonstrate the adherence to the CTP. Several IPDs are defined over 52 weeks because the primary assessment of benefit-risk of nintedanib in PF-ILD will be based on the analysis over 52 weeks (Part A). These IPDs will also be considered over the whole trial, and the respective summary will be presented as well in the CTR.

Table 6.2: 1 Important protocol deviations

Category/Code		Description	Requirements	Excluded from
A		Entrance Criteria Not Met		
	A1	Inclusion criteria not met		
	A1.1	Male or female patients aged \geq 18 years at Visit 1	Inclusion criterion 2 not met (or other age restriction specified as per a local amendment) Automatic IPD	None
	A1.2	At least one criteria for PF-ILD fulfilled within 24 months of Visit 1 despite treatment with unapproved medications used in clinical practice to treat ILD	Inclusion criteria 3a, 3b, 3c or 3d not met Automatic IPD Additional note: Requirement for treatment with unapproved medications is relative, and does not apply for all ILDs. Therefore lack of previous therapy is NOT to be considered for this IPD	None
	A1.3	Extent of lung fibrosis $> 10\%$ on HRCT performed within 12 months of Visit 1	Inclusion criterion 4 not met; or extent of fibrosis $\leq 10\%$ according to database (evaluated by central review) Automatic IPD Additional note: If the HRCT scan is older than 12 months but it is read by the central review, the case is not an IPD. Similarly, if the image acquisition criteria are not met but the image was read, the case is not an IPD.	None
	A1.4	For patients with underlying connective tissue disease (CTD): stable CTD as defined by no initiation of new therapy or withdrawal of therapy for CTD within 6 weeks prior to Visit 1.	Inclusion criterion 5 not met. Automatic IPD Additional note: Any change in CTD therapy within 6 weeks prior to Visit 1 is to be considered as IPD.	None

Table 6.2: 1 Important protocol deviations (continued)

Category/Code	Description	Requirements	Excluded from
A2	Exclusion criteria met		
A2.1	
Patient has laboratory values that indicate additional risk at Visit 1:
 
 a) >1.5xULN for AST or ALT b) >1.5xULN for Bilirubin c) Creatinine clearance < 30 ml /min (Cockcroft-Gault formula) 	
Laboratory values out of tolerated ranges at visit 1 according to the database:
 
 a) 1.5xULN for AST or ALT (exclusion criterion 1 not met) b) 1.5xULN for Bilirubin (exclusion criterion 2 not met) c) Creatinine clearance < 30 ml /min (Cockcroft-Gault formula) (exclusion criterion 3 not met) 
Automatic IPD
 
Additional note: In the CTR Table it should show which criteria are violated; however, deviations of multiple sub-categories will only counted once towards the overall category.
	None
A2.2	
Patient with other underlying diseases, conditions or risks which are excluded as per clinical trial protocol
 
 a) chronic liver disease (Child Pugh A, B or C hepatic impairment) b) IPF c) Significant pulmonary Arterial Hypertension d) Major extrapulmonary physiological restriction e) Cardiovascular disease within 6 months of Visit 1 f) Bleeding risk g) History of thrombotic events within 12 months of Visit 1 h) Known hypersensitivity to the trial medication or its components i) Peanut allergy 	
Patients who:
 
 a) suffer from chronic liver disease (Child Pugh A, B or C) (exclusion criterion 4 met) b) are diagnosed with IPF (exclusion criterion 8 met) c) show significant pulmonary arterial hypertension (exclusion criterion 9 met) d) show major extrapulmonary physiological restriction (exclusion criterion 12 met) or according to central review (“are there any co-existing HRCT features that would exclude this patient” is ticked with “yes”) e) have a history of cardiovascular disease within 6 months of Visit 1 (exclusion criterion 13 met) f) have extended bleeding risk (exclusion criterion 14 met) g) have a history of thrombotic events within 12 months of Visit 1 (exclusion criterion 15 met) h) have a known and documented hypersensitivity to the trial medication or its components (exclusion criterion 16 met) i) have a known and documented peanut allergy (exclusion criterion 17 met) at visit 1. 
Automatic IPD
 
Additional note: In the CTR Table it should show which criteria are violated; however, deviations of multiple sub-categories will only counted once towards the overall category.
	None

Table 6.2: 1 Important protocol deviations (continued)

Category/Code	Description	Requirements	Excluded from	
A2.3	Forbidden previous therapy as per clinical trial protocol a) Previous treatment with nintedanib or pirfenidone b) Other investigational therapy received within 1 month or 6 half-lives (whichever greater) prior to Visit 1 c) Any of the following medications for the treatment of ILD: azathioprine (AZA), cyclosporine, mycophenolate mofetil (MMF), tacrolimus, oral cortico-steroids (OCS) >20mg/day and the combination of OCS + AZA + n-acetylcysteine (NAC) within 4 weeks of Visit 2, cyclophosphamide within 8 weeks of Visit 2, rituximab within 6 months of Visit 2	
Patients who have:
 
a) ever been treated with nintedanib or pirfenidone (exclusion criterion 5 met) b) received other investigational therapy within 1 month or 6 half-lives (whichever greater) prior to Visit 1 (exclusion criterion 6 met) c) used azathioprine, cyclosporine, MMF, tacrolimus, OCS >20mg/day and the combination of OCS+AZA+NAC within 4 weeks of Visit 2, cyclophosphamide within 8 weeks of Visit 2, rituximab within 6 months of Visit 2 (exclusion criterion 7 met)
 
Manual IPD based on exclusion criteria and / or to be identified at the site level on the manual PD log
 
Additional note: In the CTR Table it should show which criteria are violated; however, deviations of multiple sub-categories will only counted once towards the overall category.
	None	
A2.4	Potential risk related to fetotoxicity	
Women who fulfil the following criteria at Visit 1 and:
 
a) are pregnant, nursing, or who plan to become pregnant while in the trial (exclusion criterion 21 met) b) are of childbearing potential not willing or able to use highly effective methods of birth control per ICH M3 (exclusion criterion 22 met)
 
Automatic IPD
 
Additional note: In the CTR Table it should show which criteria are violated; however, deviations of multiple sub-categories will only counted once towards the overall category.
	None	
B	Informed Consent			
	B1	Informed consent not given	
Inclusion criterion 1 not met
 
Automatic IPD
	All

Table 6.2: 1 Important protocol deviations (continued)

Category/Code	Description	Requirements	Excluded from
	B2	
Informed consent given too late
 
eCRF date of informed consent is after date of Visit 1
 
Automatic IPD
 
Additional note: Signature of the wrong IC version, and later signature of the correct one will also be part of this IPD category. This can however only be determined via a manual process.
	None
	B3	
Informed consent not given or withdrawn for optional HRCT but optional HRCT done
 
According to HRCT database and eCRF page informed consent for optional HRCT
 
Manual IPD
	None
C	Trial medication and randomisation		
	C1	
Incorrect trial medication taken between baseline and Week 52
 
Medication taken (between randomisation and Week 52) that is not matching the treatment a patient was randomised to.
 
This can only be determine after unblinding. Programming support for listing generation needed, but a manual allocation process.
 
Additional note: In the CTR Table only the deviation itself will be shown, additional information (e.g. dose level, time point, duration of the wrong medication intake, etc) will be part of a listing.
	None
	C2	
Randomisation not followed
 
The wrong medication kit is given, leading to the patient taking treatment different from the one randomised by IRT at time of randomisation (Visit 2).
 
This can only be determine after unblinding. Programming support for listing generation needed, but a manual allocation process
 
Additional notes: This is only an IPD if the medication error leads to an actual treatment switch.
	None

Table 6.2: 1 Important protocol deviations (continued)

Category/Code	Description	Requirements	Excluded from
C3	Overall compliance between randomisation and Week 52 not between 80% and 120% inclusive (or noncompliance based on investigator assessment)	In case calculated overall compliance is missing: If the answer to the question "Did the patient take trial medication as instructed?" of the eCRF is "No" at at least one of the visits where the compliance cannot be calculated, then an IPD will be flagged. Otherwise no IPD although calculated overall compliance is missing. Automatic IPD with review of MQRM listings	None
C4	Trial medication not interrupted when ALT or AST \geq 5 fold ULN	Based on eCRF dose interruption and adverse event pages between first drug intake and and Week 52 Manual IPD	None
C5	Trial medication not permanently discontinued after signs of liver enzyme elevations were observed that a) are indicative of hepatic injury as defined in Section 5.3.6.1 of the CTP b) correspond to ALT or AST \geq 3 fold ULN despite dose reduction or treatment interruption for 2 weeks or more	All patients where signs of liver enzyme elevations are not dealt with according to the requirements of the CTP. Programmatic support will be required to flag patients who may fulfil the criteria, however a manual review of outputs is required Additional note: In the CTR Table it should show which criteria are violated; however, deviations of multiple sub-categories will only counted once towards the overall category..	None

Table 6.2: 1 Important protocol deviations (continued)

Category/Code	Description	Requirements	Excluded from
D	Concomitant Medication		
D1	Patients who received either azathioprine, cyclosporine, tacrolimus, Rituximab, Cyclophosphamide, mycophenolate mofetil, OCS >20mg/day for the treatment of ILD or CTD: a) within the first 6 months of study treatment b) after 6 months of study treatment without significant deterioration of ILD or CTD	
Patients should be flagged programmatically who take any of the aforementioned medications. It would have to be manually checked if:
 
a) Any of these medications is used during the first 6 months of study AND NO documentation of exacerbation of ILD is provided; or if the medication is used for the treatment of the CTD.
 
b) Any of these medications is used after 6 months of study medication AND NO documentation of worsening of the ILD or exacerbation of ILD is provided; or no documentation of worsening of the CTD is provided
 
Programmatic support will be required to flag patients who may fulfil the criteria, however a manual review of outputs is required
 
Additional note: In the CTR Table it should show which criteria are violated; however, deviations of multiple sub-categories will only counted once towards the overall category
	None
D2	Patients who received either pirfenidone, nintedanib (in another occurrence than as study medication) or any other investigation drug during the entire duration of their study participation.	
Any occurrence of such concomitant therapy is to be flagged as IPD.
 
Automatic IPD
 
Additional note: In the CTR Table it should show which medication was taken; however, deviations regarding multiple medications will only counted once towards the overall category.
	

Automatic PDs are those detected via an automated programming process using SAS®.

6.3 PATIENT SETS ANALYSED

- Screened set (SCS):
 - This patient set includes all patients having signed informed consent.
- Randomised set: (RS)
 - This patient set includes all randomised patients, whether treated or not.
- Treated set (TS):
 - This patient set includes all randomised patients who received at least one dose of trial medication. The TS also reflects the “the overall population” for the analyses and is considered as one of the two co-primary populations.
 - The subpopulation of patients with “HRCT with UIP-like fibrotic pattern only” (actual HRCT pattern as documented in the eCRF) is considered as the second co-primary population.
 - The subpopulation of patients with “other HRCT fibrotic patterns” (actual HRCT pattern as documented in the eCRF) is referred to as complementary population
- PK set (PKS)
 - This patient set includes those patients in the TS with at least one valid plasma concentration available

Please note: Details on which set or population is used for which analysis and output can be found in this statistical analysis plan.

6.4 SUBGROUPS

The subgroups listed in [Table 6.4: 1](#) will be investigated, provided that the:

- actual size of the individual subgroup expression level is large enough (>10% of the treated patients)
- distribution of patients within subgroup expression level across the two treatment arms

allow for meaningful analyses. Groups that are too small will be pooled in a meaningful manner. Selected variables as defined in [Section 5.4](#) will be used to characterize the study population in all subgroups. In addition, evaluations will be performed to determine efficacy as well as safety in these pre-selected subgroups. For more details on the planned analysis, please refer to [Section 7.4.3](#).

Table 6.4: 1 Subgroup analyses – List of subgroups

	Description of study population [1][2]	Efficacy analyses on the primary endpoint in the overall population [1][3]	Safety analyses in the overall population [1][3]
Gender (Male / Female)	X	X	X
Age (<65 / ≥65)	X	X	X
Race ^[4] (White / Asian / Black or African American)	X	X	X
Baseline FVC % predicted (≤70% / >70%)	X	X	X
Underlying clinical ILD diagnosis (Hypersensitivity pneumonitis / Idiopathic nonspecific interstitial pneumonia / Unclassifiable idiopathic interstitial pneumonia / Autoimmune ILD ^[5] / Other ILDs ^[6])	X	X	X
Baseline bodyweight (≤65kg / >65kg)	X		X
Patients receiving / not receiving DMARDs with known hepatotoxic effects at baseline	X		X
Patients receiving / not receiving DMARDs with known gastrointestinal effects at baseline	X		X
Methotrexate use at baseline (Yes / No)	X		X

[1] For more details regarding analyses, please refer to [Table 7.4.3: 1](#).

[2] The description of study population for all described subgroups will be provided for the two co-primary populations as well as for the complementary population

[3] Please note that the primary endpoint analyses and safety analyses by subgroup will also be performed in the co-primary population of patients with “HRCT with UIP-like fibrotic pattern only” for gender, age and race

[4] Please note that only single race respondents are taken into account. “American Indian or Alaska Native” patients, or patients that classify themselves as “Native Hawaiian or other Pacific Islander”, are pooled with “Asian” patients in the subgroup evaluations, due to the very low number of patients in those expression levels.

[5] For the purpose of the subgroup analysis based on grouped clinical ILD diagnoses, a new category of “Autoimmune ILDs” was created. This category includes all cases from the individual eCRF categories of “Rheumatoid Arthritis associated ILD”, “Systemic sclerosis associated ILD”, “Mixed connective tissue disease” as well as cases identified as “autoimmune ILD” from the eCRF category of “Other fibrosing ILD” (see [Table 9.13: 1](#) for details). The classification of these cases in the eCRF category “Other fibrosing ILD” was reviewed and confirmed by the Steering Committee.

[6] For the purpose of the subgroup analysis based on grouped clinical ILD diagnoses a new category of “Other ILDs” was created. This category includes all cases from the individual eCRF categories of “Exposure-related ILD”, “Sarcoidosis” as well as cases identified as other ILD (“other ILD” and “exposure-related ILD” – see [Table 9.13: 1](#) for details) from the eCRF category of “Other fibrosing ILD”. The classification of these cases in the eCRF category “Other fibrosing ILD” was reviewed and confirmed by the Steering Committee

6.5 POOLING OF CENTRES

This section is not applicable because centre/country is not included in the statistical model.

6.6 HANDLING OF MISSING DATA AND OUTLIERS

In general, missing data will not be imputed. Exceptions are detailed in the subsequent subsections.

Two patients with non-determined HRCT pattern by central readers were randomised by mistake, and those patients will generally be evaluated according to the information used

during their randomisation in the IRT system (“other HRCT fibrotic patterns” for both patients) in all analyses considering the actual HRCT pattern, including the primary analysis. They will be evaluated as “Patients with HRCT with UIP-like fibrotic pattern only” in the sensitivity analysis investigating the potential effect of mis-stratification.

6.6.1 Primary endpoint

The statistical model used for primary analysis (see Section 7.3.1 of CTP) allows for missing data, assuming they are missing at random (MAR). Even patients with only one post-baseline assessment can be included in the model and can therefore participate in variance estimation. The statistical model assumes that patients who prematurely discontinue study participation would have behaved similarly to those who remained in the study.

Sensitivity analyses using alternative assumptions will be conducted to investigate the potential effect of missing data on the results of the primary analysis (see [Section 7.4.2](#) and [Section 9.12.1](#)).

6.6.2 Secondary and further endpoints

6.6.2.1 Change from baseline endpoints

The statistical Mixed effect Model for Repeated Measures (MMRM) used for the analysis of continuous secondary endpoints allows for form-level missing data, assuming they are missing at random. Item-level data for the PRO measures will be handled according to the instructions provided by the instrument developer.

6.6.2.1.1 K-BILD

Missing item scores are imputed based on the average of the non-missing item scores within the domain, rounded to the nearest integer. If the missing items are >50% per domain, then the domain score is set to missing. If item 15 is missing, it will be replaced by the average of all available items 1-14. If any of the domain scores are missing, the total score is set to missing.

6.6.2.1.2 L-PF

The L-PF scores represent means. Missing items are generally not counted in the denominator. Please note the following exception for the Dyspnea score items 1, 2.4-10 and 12

- If “No” is ticked and “B” is ticked, then the item is not scored and does not contribute to the denominator.
- if “No” is ticked and neither “A” nor “B” is ticked, the item is counted as missing BUT the item DOES contribute to the denominator

If the missing items are $\geq 50\%$ within a score, then the corresponding score is set to missing.

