 3. EQ-5D
 4. PF-IQOLS
- Urine pregnancy test and any laboratory sample collection must be performed prior trial medication administration.
- FVC and DLCO measurement at all visits should be performed approximately at the same time of the day to reference time point at Visit 2.
- Order of pulmonary function tests must always be
 1. FlowScreen® spirometry (FVC) followed by patient's rest
 2. DLCO with site's own equipment.

Baseline Visit 2 (randomization)

The following prerequisites must be available for randomization:

- Eligibility confirmation and HRCT pattern from central HRCT review.
- Safety laboratory results including haemoglobin and creatinine from Visit 1.

Procedures:

- All patients will be asked to fill out the patient reported outcome questionnaires prior to any other visit procedure. The order of the questionnaires will always be: 1. K-BILD, 2. L-PF Symptoms and Impact Questionnaire, 4. EQ-5D, 5. PF-IQOLS.
- Site personnel will review questionnaires for completeness.
- Physical examination including vital signs and HCRU interview will be performed.
- Adverse events and concomitant therapy since last visit will be reviewed and recorded.
- Medical history will be reviewed.
- Repeated resting 12-lead electrocardiogram using site's own equipment will be performed and evaluated if resting ECG was abnormal at Visit 1 (if possible prior to blood draw).
- SpO₂ will be recorded (earlobe or forehead, resting).
- FVC measurement will be conducted with the FlowScreen® spirometer.
- DLCO measurement with sites own equipment will be conducted.
- All in/exclusion criteria will be assessed based on Visit 1 laboratory and Visit 2 measures.
- HRCT will be performed in patients who agree to have follow-up HRCT done as part of the trial, unless a screening HRCT was done as part of the study to determine eligibility.

- Safety blood and urine samples will be collected and submitted to the central laboratory.
- Biomarker samples will be collected and submitted to the central laboratory.
- The time of blood collection for biomarker samples will be recorded in the eCRF.
Note: blood samples should always be collected prior to drug administration.
- One blood sample for DNA banking will be collected in eligible patients and only after obtaining a separate informed consent.
- Local urine dipstick pregnancy test (if applicable).
- If a patient is eligible for the trial, randomization will be performed by using the IRT system.
- Treatment will be dispensed.

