B Not applicable, because I did not want or have the opportunity to do it

11. Over the last 24 hours, how short of breath were you after eating a meal or snacks?

Not at all 0 1 2 3 4 Extremely

12. Did you lift and carry a light load (e.g., less than 10 lbs) a short distance (e.g., from one room to another) in the last 24 hours?

Yes How short of breath did lifting and carrying a light load a short distance make you?

Not at all 0 1 2 3 4 Extremely

No I did not lift or carry a light load a short distance in the last 24 hours because:

A I avoided this activity because it was too difficult to perform

B Not applicable, because I did not want or have the opportunity to do it

Items 13-18: Each item focuses on cough. Again, reflect on the last 24 hours as you consider where you are on the scale between the two statements.

13. Over the last 24 hours, how often did you cough?

Not at all 0 1 2 3 4 Constantly

If you chose "0", please skip to Item 18.

14. Over the last 24 hours, how often did you cough when you took a deep breath?

Not at all 0 1 2 3 4 Constantly

15. Over the last 24 hours, how often did you cough when you were breathing hard or fast?

Not at all 0 1 2 3 4 Constantly

16. Over the last 24 hours, how often did you cough when you over-exerted yourself?

Not at all 0 1 2 3 4 Constantly

17. Over the last 24 hours, how often did coughing make you short of breath?

Not at all 0 1 2 3 4 Constantly

18. Over the last 24 hours, how often did you feel an annoying tickle in your throat?

Not at all 0 1 2 3 4 Constantly

19-23: These items primarily focus on your energy level. Again, reflect on the last 24 hours as you consider where you are on the scale between the two statements.

19. Over the last 24 hours, how was your energy level?

Extremely low 0 1 2 3 4 Excellent

20. Over the last 24 hours, of all that you wanted to get done, how much did you actually get done?

Nothing 0 1 2 3 4 Everything

21. Over the last 24 hours, how much energy did you have to do all the things you like to do?

No energy 0 1 2 3 4 A lot

22. Over the last 24 hours, how much did coughing have a negative effect on your energy?

No effect at all 0 1 2 3 4 A lot

23. Did you become short of breath in the last 24 hours?

Yes How long did it take you to recover when you became short of breath?

No time at all 0 1 2 3 4 An extremely long time

No Please continue to the next page.

Thank you for taking the time to complete the L-PF Symptoms Questionnaire.

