6.7 BASELINE, TIME WINDOWS AND CALCULATED VISITS

As a general rule, the last assessment / measurement observed prior to start of trial medication will be assigned to baseline. Note that for some trial procedures (e.g. body weight, vital signs, laboratory tests) this may be the value measured on the same day trial medication was started. In these cases it will be assumed that the measurements were taken prior to the intake of any study medication (if the measurement time was not captured). If no further data available, this can also be the last screening assessment.

Visit windowing will be performed as described in [Table 6.7: 1](#), [Table 6.7: 2](#), [Table 6.7: 3](#) and [Table 6.7: 4](#), in order to assign data to the relevant study visit based on the actual day of the assessment. Data will be analysed using the re-calculated visits in the statistical tables. However, in the listings, all visits performed will be displayed (even if outside time-window), along with the re-calculated visit.

Table 6.7: 1 Time windowing rules for spirometry (FVC), physical exam, vital signs

Time window of actual day ^[1]			Allocated to		
Start (S _n) day	End (included) (E _n) day	Length of the time-window [days]	Visit number (n)	Visit name	Planned day of the visit (V _n)
-84	1	85	2	Baseline	1
2	22	21	3	2 weeks	15
23	36	14	4	4 weeks	29
37	64	28	5	6 weeks	43
65	127	63	6	12 weeks	85
128	211	84	7	24 weeks	169
212	309	98	8	36 weeks	253
310	373	64	9	52 weeks	365
374 (S _p)	E _p = (V _p + V _{p+1})/2 = 533	E _p -S _p +1 = 160	10	68 weeks	477 (V _p)
E _p + 1	(V _{p+1} + V _{p+2})/2	E _{p+1} -S _{p+1} +1	11	84 weeks	589 (V _{p+1})
...	Every weeks thereafter	16
					...

^[1] First trial drug intake date is taken into account as a reference to calculate time windows

Table 6.7: 2 Time windowing rules for K-BILD, L-PF, PF-IQOLs, SpO₂

Time window of actual day ^[1]			Allocated to		
Start day	End day (included)	Length of the time-window [days]	Visit number	Visit name	Planned day of the visit
-84	1	85	2	Baseline	1
2	127	126	6	12 weeks	85
128	211	84	7	24 weeks	169
212	309	98	8	36 weeks	253
310	373	64	9	52 weeks	365

^[1] First trial drug intake date is taken into account as a reference to calculate time windows

Note: SpO₂ not measured at visits 6 and 8

Table 6.7: 3 Time windowing rules for DLCO

Time window of actual day ^[1]			Allocated to		
Start (S _n) day	End (included) (E _n) day	Length of the time-window [days]	Visit number (n)	Visit name	Planned day of the visit (V _n)

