7.5.2.2.4 Living with Pulmonary Fibrosis Symptoms and Impact Questionnaire (L-PF)

The absolute change from baseline in L-PF symptoms dyspnoea domain score between week 52 and baseline will be presented graphically as well as numerically to illustrate the impact of the underlying condition on the patient's health status.

The absolute change from baseline in L-PF symptoms cough domain score between week 52 and baseline will be presented graphically as well as numerically to illustrate the impact of the underlying condition on the patient's health status.

The descriptive analyses of the absolute change from baseline in L-PF symptoms dyspnoea domain score as well as L-PF symptoms cough domain score will also be shown for the complementary population.

In addition to the descriptive evaluation, absolute change from baseline in L-PF symptoms dyspnoea domain score between week 52 and baseline, as well as in L-PF symptoms cough domain score between week 52 and baseline will also be analysed using a restricted maximum likelihood (REML) based repeated measures approach. An unstructured variance-covariance structure will be used to model the within patient measurements. In the event of non-convergence, the same methods used in the primary analyses ([Section 7.4.1](#)) will be implemented to overcome the issue. The HRCT pattern will be included as a covariate (with exception when the analysis is run in the co primary population of patients with "HRCT with UIP-like fibrotic pattern only") as well as the respective baseline L-PF symptoms score.

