9.2.1.2 Cough (items 13-18)

$$\text{Cough Symptom Score} = \frac{\text{sum of responses from items 13 - 18}}{24} \times 100$$

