9.2.1.3 Energy (items 19-23)

For items 19-22:

- scores equal whichever box is ticked (0-4)

For item 23:

- if “Yes” is ticked, score equals whichever box is ticked (0-4)
- if “No” is ticked, the item is not scored and does NOT contribute to denominator

$$\text{Energy Symptom Score} = \frac{\text{sum of responses from items 19 - 23}}{\text{total score possible (20 or 16 if response for 23 is "No")}} \times 100$$

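### As written, the SAP sets the L-PF cough score to missing when a patient reports no cough, and it sums reverse-worded L-PF items unreversed, so the Fatigue score runs backwards on net

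*SAP*

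**What the plan says.** **Cough.** Change from baseline to week 52 in the L-PF Symptoms cough score is an other secondary endpoint (Protocol 5.1.2, SAP 4.3).

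- On the form (Protocol Appendix 10.3.2), a patient who answers 0 on item 13 is told "please skip to Item 18".
- SAP 6.6.2.1.2 leaves missing items out of the denominator in general. If 50% or more items are missing "within a score, then the corresponding score is set to missing". Its listed exceptions concern Dyspnea items only.
- SAP 9.2.1.2 sums items 13-18 and divides by a fixed 24, with no rule for skipped items.
- SAP 9.2.1.3 does have such a rule for item 23: after a 'No', "the item is not scored and does NOT contribute to denominator".
- The model in SAP 7.5.2.2.4 is for change from baseline. It adjusts for HRCT pattern "as well as the respective baseline L-PF symptoms score".

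**Direction.** SAP 5.2.2.2.4 gives L-PF scores a 0-100 range in which higher means more impaired. The form prints Symptoms items 19-21 and Impacts items 3 and 17-21 with 4 as the best answer. For items 19-22, SAP 9.2.1.3 says "scores equal whichever box is ticked (0-4"). Sections 9.2.2.1 and 9.2.2.4 sum the Impacts responses and mention no recoding.

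**Outside source.** SAP 6.6.2.1 says item-level data follow the instrument developer's instructions. Those instructions are not reproduced.

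**The concern.** The two cough rules give different results for one correctly completed form, and the 50% rule is triggered by the best possible answer to the lead cough question. Whether the week-52 score is missing then depends on the week-52 value itself, while the MMRM treats missing data as missing at random.

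The loss also reaches baseline. Without a baseline score there is no change score and no covariate, so the patient leaves the cough analysis at every visit. The screening fallback in SAP 6.7 ("If no further data available, this can also be the last screening assessment") does not help. The questionnaires belong to the Visit 2 procedures in Protocol 6.2.2 ("All patients will be asked to fill out the patient reported outcome questionnaires prior to any other visit procedure") and are not listed for Visit 1 in 6.2.1.

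For forms completed as instructed, observed week-52 changes would therefore come only from patients who cough at both time points. Loss of cough and new cough would both be left out.

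The direction fault is separate. Items that run in opposite directions are added together, so a patient whose energy worsens can receive a better Fatigue score.

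**Working it through.** **Stated divisors.** With a maximum of 4 per item:
- Cough: 6 × 4 = 24.
- Energy: 5 × 4 = 20, or 4 × 4 = 16 if item 23 is 'No'.
- Impacts components: 24, 20, 8 and 32.

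All agree with SAP 9.2.

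**Cough, item 13 = 0**
- Blank items: 14, 15, 16 and 17. Share blank = 4/6 = 66.7%, above 50%, so the score is missing under 6.6.2.1.2.
- Under 9.2.1.2 the score is item 18/24 × 100. For item 18 = 0, 1, 2, 3, 4 this gives 0, 4.2, 8.3, 12.5, 16.7.
- Dropping the blanks from the denominator but ignoring the 50% rule gives item 18/8 × 100, that is 0 to 50.
- Example: all six items at 2 at baseline give 12/24 × 100 = 50. With items 13 and 18 both 0 at week 52, the change is −50 under 9.2.1.2 and missing under 6.6.2.1.2. The reverse course (+50) is excluded at every visit.

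**Possible extent (assumptions; the documents give no response distribution)**
- If 5%, 10%, 20% or 30% of the 600 planned patients answer 0 on item 13 at week 52, then 30, 60, 120 or 180 lose that score.
- Treatment difference left out of the observed data = (difference between arms in cough-free share) × (gap in change between cough-free and other patients), with the other patients assumed to change equally in both arms. For shares differing by 5 to 10 percentage points and gaps of 30 to 50 points: 0.05 × 30 = 1.5, 0.05 × 50 = 2.5, 0.10 × 30 = 3.0, 0.10 × 50 = 5.0. This is before the MMRM recovers anything from earlier visits.

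**Energy (the Fatigue domain, by elimination among the three Symptoms domains)**
- Best answers on items 19-23 (4, 4, 4, 0, 0): 12/20 = 60. If item 23 is 'No': 12/16 = 75.
- Worst answers (0, 0, 0, 4, 4): 8/20 = 40.
- Moving from best to worst should be +100. As written it is 40 − 60 = −20, or 40 − 75 = −35, which reads as an improvement.
- One step worse on all five items changes the score by (−3 + 2)/20 × 100 = −5.
- With items 19-21 scored as 4 minus the ticked value, best is 0 and worst is 100.

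**Effect on the totals (uniform best and worst answers)**
- Global Impact: best 20/32 = 62.5, worst 12/32 = 37.5.
- Dyspnea Impact: best 4/24 = 16.7, worst 20/24 = 83.3.
- Impacts total: best (16.7 + 0 + 0 + 62.5)/4 = 19.8, worst (83.3 + 100 + 100 + 37.5)/4 = 80.2.
- Symptoms total, best: (0 + 0 + 60)/3 = 20, or (0 + 0 + 75)/3 = 25 if item 23 is 'No', with cough taken as 0.
- Symptoms total, worst: (100 + 100 + 40)/3 = 80. SAP 9.2.1.1 allows 5 on ten Dyspnea items, so the Dyspnea maximum is 10 × 5 + 2 × 4 = 58. If all twelve are 4, Dyspnea is 48/58 = 82.8 and the total is (82.8 + 100 + 40)/3 = 74.3.

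Both totals are compressed but keep their direction.

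**The case against.** - **An instructed skip may not count as missing.** The SAP separates items not scored by design from missing items, for Dyspnea and for item 23. If the cough skip is read the same way, the 50% rule never applies and 9.2.1.2 already gives a sensible score. But no text extends that treatment to items 14-17. Where the SAP foresaw a by-design blank it wrote a rule, and here it did not. At best, the text supports two incompatible results.
- **The developer's instructions may settle both points.** This stands. They cannot be checked, so the finding is about the SAP as printed and not about how scores will in fact be computed.
- **Only 9.2.1.3 says explicitly that the ticked value is used.** For Impacts, the text speaks of summing responses. That is correct, but with no recoding stated, the plain reading is the same.
- **Some patients may tick 0 on items 14-17 despite the skip, and those forms would be scored.** This stands. The exclusion applies to forms completed as instructed.
- **The 1.5 to 5.0 points rest on stacked assumptions.** This stands. The arms may not differ at all, a patient cannot fall by more than the baseline score, patients without cough at both visits change little, and new cough is not in the formula. The range is illustrative only.
- **The endpoints are minor.** Cough is outside the confirmatory test, Fatigue is exploratory, and neither carries a p-value. This limits the severity, but the adjusted estimates are still to be produced.

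**Conclusion.** Both faults are present in the SAP as written. They should be fixed, but they do not threaten the trial's main conclusion.

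**Cough:** a form showing no cough is missing under 6.6.2.1.2 and scores 0 to 16.7 under 9.2.1.2. Missingness tied to the value itself strains the missing-at-random assumption. The direction of any bias depends on which arm has more cough-free patients. Its size cannot be stated without the share answering 0 on item 13.

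**Direction:** Fatigue is the only endpoint reversed on net, and only when its items move together; a change confined to items 22-23 is scored correctly. Global Impact is also reversed on net but is not an endpoint. The secondary Dyspnea and Cough Symptoms scores contain no reverse-worded items.

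The primary endpoint and K-BILD are unaffected. Confidence is high for what the SAP text says and conditional on the unseen developer instructions for what would be computed.

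**What to change.** Before unblinding, check SAP 6.6.2.1.2 and 9.2 against the developer's instructions, and write the relevant rules into the SAP. Settling this after unblinding would leave the choice of scoring rule open to the data. Unless those instructions say otherwise:

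1. When item 13 = 0, score items 14-17 as 0 and exempt them from the 50% rule, at baseline and at later visits. Keep the divisor of 24.
2. In 9.2.1.3, 9.2.2.1 and 9.2.2.4, score Symptoms items 19-21 and Impacts items 3 and 17-21 as 4 minus the ticked value before summing.
3. Report, by arm and visit, how many patients answered 0 on item 13.

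The cost is a few lines of SAP text and scoring code plus one count table. No new data are needed.
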